6.5 POOLING OF CENTRES

Part 1 of this study is planned to be carried out in approximately 35 centres. However, not all centres have the same SOC procedures. During the course of the study, and gathering information (retrospectively) from each of the centres with regard to their SOC procedures, they will be grouped into relatively homogeneous groupings.

Because the groupings will only be made after randomisation of a patient within a centre, this will be a retrospective and exploratory analysis, albeit planned. It is planned only to investigate the primary endpoint with this centre grouping in a sensitivity analysis – See [Section 7.4.2](#).

6.6 HANDLING OF MISSING DATA AND OUTLIERS

All efforts will be made to avoid having missing data in the database, however it is inevitable that there will be missing data, by design:

- For patients that die, there will be no further data.
- For patients that are discharged from hospital before day 28, the only additional efficacy assessment is the vital status at days 28 and 90.
- For the daily average PaO₂/FiO₂ ratio at Day 6: if no value available due to hospital discharge, then use value at hospital discharge; if no value available due to death then do not impute but handle as failure in analysis to determine difference in median with 95% CI. Otherwise, outcome unknown and not included in denominator.

- For SOFA improvement: if no value available due to hospital discharge the improvement=yes; if no value available due to death then improvement=No; if missing components but assessment conducted, the previous components can be carried forward; if day 5 value available then this can be used in place of day 6; then improvement from baseline determined. Otherwise, outcome unknown and not included in denominator.
- For Evolution of APACHE II and daily average PaO₂/FiO₂: carry forward missing APACHE II components if possible (APACHE II); otherwise no imputation but present the number of cumulative hospital discharges and cumulative deaths in the same table.

Missing or incomplete adverse event (AE) dates will be computed using the BI handling rules ([4](#)).

6.7 BASELINE, TIME WINDOWS AND CALCULATED VISITS

Randomisation is defined as Day 1 and it is planned that the alteplase patients are administered their initial 2h infusion of study medication within 6 hours of randomisation, on Day 1 (Visit 2a). The last planned administration of study medication for the alteplase patients is the long term 12h infusion on Day 5.

Since all patients are on SOC and there is no clear start or stop of SOC, a fixed treatment duration will be used for all patients, for the purposes of the analyses. Therefore, endpoints referred to as 'on treatment' will include all relevant events from the relevant start point plus 288 hours (last planned treatment on Day 5 + 7 days of REP = 12 days = 288 hrs). The starting point for the alteplase patients is date and time of first administration of alteplase, whilst the starting point for the SOC patients is the date and time of randomisation. For alteplase patients which have more than 5 days of infusion, the end date of 'on treatment' will be the date and time of last intake of alteplase plus 168h (=7 days).

According to CTP Section 1.2, the residual effect period (REP) is 7 days.

According to CTP Section 7.2.1, the term "baseline" refers to the last observed measurement prior to randomisation on Day 1, which will be Visit 1, the screening visit. It cannot be determined with certainty if a value measured on Day 1 is prior to randomisation, so the screening value will be used consistently throughout. Only if otherwise indicated, will the assessment on Day 1 be used, where the time of the assessment can be compared to the time of the randomisation.

7. PLANNED ANALYSIS

The tables that are created from the statistical analysis will follow the format of the standard within BI ([5](#)).

The overall disposition of the patients in the trial will be presented, together with the number of patients discontinuing prior to day 28, and vital status at day 90.

The number of patients participating in the study by country and the number of sites, for each of the patient populations will be summarised.

Demography and baseline characteristics will be presented, as well as the stratification used at the time of the patient randomisation.

A summary of the iPDs will be provided.

Where statistical comparisons are indicated, they will be done by comparing the following groups:

- alteplase low versus SOC
- alteplase high versus SOC

For efficacy analyses, patients will be analysed according to the patient information (ventilation status) given in the CRF (NIV / MV), in the case of potentially erroneous data entered into the interactive recognition technology (IRT).

In general, for End-Of-Text tables, the set of summary statistics is: N (number of patients with non-missing values) / Mean / SD / standard error (SE) / Min / Q1 (lower quartile)/ Median / Q3 (upper quartile)/ Max.

Statistical parameters will be displayed to a defined number of decimal places as specified in the BI guideline "Reporting of Clinical Trials and Project Summaries" ([6](#)).

Tabulations of frequencies for categorical data will include all possible categories and will display the number of observations in a category as well as the percentage (%) relative to the respective treatment group (unless otherwise specified, all patients in the respective patient set whether they have non-missing values or not). Percentages will be rounded to one decimal place. The category missing will be displayed only if there are actually missing values.

7.1 DEMOGRAPHIC AND OTHER BASELINE CHARACTERISTICS

Only descriptive statistics are planned for this section of the report. See [Section 5.4](#) for specific definitions.

7.2 CONCOMITANT DISEASES AND MEDICATION

Medical history, COVID-19 signs and symptoms and concomitant diagnoses will be presented and coded using MeDRA System Organ Class and Preferred Term where possible.

Regarding concomitant medications, there is a specific question asking if the treatment belongs to standard of care, which is relevant for all patients since they all receive SOC in the background. This question is different to the randomised treatment assignment. Therefore, all concomitant medication analyses or displays will be split by 'Standard of Care use' and 'non-Standard of Care use'. All concomitant medications will be coded using the WHO Drug dictionary.

Medications of special interest for COVID (as indicated by WHO, see [Section 9.1](#)), and restricted medications within this study (as outlined in CTP Section 4.2.2.1, see [Section 9.2](#)) will also be summarized and split by Standard of Care use and non-Standard of Care use.

Use of heparin will be summarized and presented.

Therefore, only descriptive statistics are planned for this section of the report.

7.3 TREATMENT COMPLIANCE

Only descriptive statistics are planned for this section of the report, and due to the nature of the study, compliance will be determined for the alteplase treatment groups only

Compliance to intake of infusion will be assessed in terms of % taken, as measured by volume, at each planned infusion. Overall compliance will be as an average measure of the %taken. The detailed definitions are provided in [Section 5.4](#).

Compliance with preparation of the infusion in terms of concentration, as indicated in CTP Table 10.5 are also assessed, and detailed definitions provided in [Section 5.4](#).

7.4 PRIMARY ENDPOINT(S)

7.4.1 Primary analysis of the primary endpoint(s)

For the primary endpoint, a cox proportional hazards model will be used to estimate the hazard ratio (HR) comparing the alteplase groups to SOC. From the model, the 95% confidence intervals (CI) and corresponding Wald p-values for the HRs will be produced. The model will include fixed effects for treatment (alteplase group of interest, SOC), the randomisation stratification factor type of ventilation (NIV, MV) and age (continuous).

Baseline ventilation status (NIV/MV) and baseline status on the WHO eleven-point clinical progression scale (5, 6, 7, 8 or 9) are correlated. That is to say, NIV take on values of 5 and 6, whilst MV takes on values of 7, 8 and 9 on the WHO clinical progression scale. Of these two, only the randomisation stratification factor ventilation status will be used in the primary model to avoid over parameterising. This is not considered to be a change from the CTP, since this still includes the baseline WHO status.

Kaplan Meier estimates will be presented by treatment (low alteplase, high alteplase, SOC) for this endpoint up to Day 28, and additionally by:

- treatment and type of ventilation (NIV, MV)
- treatment and baseline status on the WHO eleven-point clinical progression scale (5, 6, 7, 8 or 9)
- treatment and age groups (<=median, >median)

From the KM estimates stratified by treatment, and at various timepoints (days 6, 8, 12, 16, 20, 24 and 28) the risk difference (RD) with 95% CI will be estimated by taking the difference of the individual probabilities. Since the observations in the two treatment groups are independent, the variance of the Kaplan-Meier probability difference is equal to the sum of the Kaplan Meier probabilities' variances found by Greenwood's method. The 95% CI of the RD is therefore calculated accordingly.

7.4.2 Sensitivity analysis, subgroup analysis, exploratory analysis of the primary endpoint(s)

Two non-confirmatory supplementary analyses will be conducted, in anticipation of the rare situation where bail-out therapy may be used (as defined in CTP Section 4.2.2). They will be performed on the FAS.

The first of these supplementary analyses will address the treatment policy estimand, whereby there is no consideration for the intake of bail-out therapy.

The second of these supplementary analyses will address a composite estimand, whereby patients receiving bail-out therapy will be censored at Day 28, rather than on the day of bail-out. Here, bail-out represents treatment failure and thereby, by definition, precludes any response after bail-out. The various scenarios are summarized in the table below.

In both cases, and in the unlikely event that a patient discontinues from the study, prior to being able to determine if he had clinical improvement or hospital discharge, or had intake of bail-out therapy or death, he will be censored at the time of withdrawal.

Table 7.4.2: 1 Censoring of the primary endpoint for the treatment policy and composite estimands

Scenarios	Treatment policy estimand	Composite estimand
Bail-out then death	Censor at D28	Censor at D28
Bail-out then failure to improve#	Censor at D28	Censor at D28
Bail-out then clinical improvement / hospital discharge	Positive event at clinical improvement / hospital discharge	Censor at D28
Bail-out then clinical improvement / hospital discharge then death	Positive event at clinical improvement / hospital discharge	Censor at D28
Clinical improvement / hospital discharge regardless of subsequent events	Positive event at clinical improvement / hospital discharge	Positive event at clinical improvement / hospital discharge
Death only, prior to D28	Censor at D28	Censor at D28
Failure to improve# by D28	Censor at D28	Censor at D28
Discontinued from study due to withdrawal of consent prior to clinical improvement / hospital discharge or Bail-out/Death	Censor at time of study discontinuation	Censor at time of withdrawal

Clinical improvement / hospital discharge refers to the first of clinical improvement or hospital discharge, whichever comes first.

#Failure to improve is failure to have clinical improvement or hospital discharge.

The analyses performed will be identical to that outlined for the primary endpoint in [Section 7.4.1.](#)

Based on the main estimand, the treatment effect will be estimated using the cox proportional hazard model, containing only treatment in the model. The HR (95%CI) and p-value estimating the unadjusted treatment effect will be produced.

The effect of the subgroups outlined in [Section 6.4](#), related to the primary endpoint, main estimand, will be assessed descriptively and using Kaplan Meier estimates.

A covariate adjusted sensitivity analysis of the primary endpoint, main estimand, will be conducted, to determine the effect of the grouping of centres according to similar types of Standard of care. This will be the same analysis as outlined in [Section 7.4.1](#) with this additional covariate.

7.5 SECONDARY ENDPOINT(S)

7.5.1 Key secondary endpoint(s)

Not applicable.

7.5.2 Secondary endpoint(s)

Secondary endpoints are defined in [Section 5.2.2](#). In all cases, standard descriptive statistics will be presented, whether the endpoint is binary or continuous.

Binary efficacy endpoints

For the binary efficacy endpoints (ACM, ACM/MV, SOFA), analysed on the FAS, the RD will be estimated between the two treatment arms using logistic regression. In addition to treatment, adjustment will be for the randomization stratification factor (NIV/MV) and age. RD and CIs (95%) for the RD will be obtained using the Delta method and the average marginal effect (AME) method.

As sensitivity analysis for each of these binary efficacy endpoints, the unadjusted treatment estimates will be produced, using the same logistic regression model containing only treatment.

Binary safety endpoint

For the binary safety endpoint MBE, analysed on the TS, there will be no adjustment for covariates. Therefore, the RD will be the difference between the two incidences and the 95% CI will be determined using the Chan and Zhang exact method.

[figure not shown]
Continuous efficacy endpoint

The change from baseline in the continuous efficacy endpoint, daily average PaO₂/FiO₂ ratio at Day 6 is considered non-parametric in nature. Missing values for missing visits will not be imputed, and left as missing. Missing values due to death or post hospital discharge will be carried out as described in [Section 5.2.2](#). The difference in medians will be presented, together with 95% CIs, based upon the methodology of Hodges-Lehmann and the Wilcoxon rank sum test. There will be no adjustment for covariates in this non-parametric analysis.

As a sensitivity analysis for this PaO₂/FiO₂ endpoint, an ANCOVA analysis adjusting for baseline ventilation status and age will be performed. For patients that have died, the last value prior to death will be used to determine the change from baseline. Note, there are expected to be very few deaths prior to Day 6. Missing values due to hospital discharge will be handled as in the main analysis.

For the continuous efficacy endpoint, number of VFDs at Day 28, there are not expected to be any missing values by definition. This endpoint will be analysed using a restricted maximum likelihood (REML) based ANCOVA comparing the number of VFDs after 28 days, by treatment. The ANCOVA model will be adjusted for the randomization stratification factor (NIV/MV) and age. The treatment difference with 95% CI will be presented.

As a sensitivity analysis for VFD at Day 28, the unadjusted treatment effect will be estimated, using the same approach as the main analysis, but with only treatment in the model. In addition, subgroup analyses of VFD at Day 28 will be conducted using the subgroups as outlined in [Section 6.4](#). An ANCOVA model will contain the subgroup and the interaction between subgroup and treatment.

7.7 EXTENT OF EXPOSURE

Exposure will be handled descriptively.

The number of patients with initial 2h infusion on day 1, optional 2h between days 2 and 5, and longterm 12h infusion over the five days of treatment will be summarized, as well as the rate of infusion (mL/kg/h) and duration of infusion (h).

The cumulative exposure will be presented, in terms of Total number of days of infusion. Exposure is relevant for the alteplase treatment groups only.

7.8 SAFETY ANALYSIS

The safety analysis will be performed as outlined in the CTP, according to BI standards and on the TS. For further details please see guideline 'Handling and summarization of AE data for clinical trial reports and integrated summaries' ([7](#)).

The definition of 'on treatment' is outlined in [Section 6.7](#). Any potential events starting between the time of randomization and the start of alteplase treatment, will be indicated as such in the listings.

In addition, to fulfil the requirements of the European Union (EU) Regulation 536/2014 (Annex V, Point 6) ([8](#)), the following information should be made available, for the lay summary or CTR:

- frequency of serious drug-related AEs by treatment, primary system organ class and preferred term.

7.8.1 Adverse Events

Unless otherwise specified, the analyses of AE will be descriptive in nature. All analyses of AEs will be based on the number of subjects with AEs and NOT on the number of AEs.

AEs will be coded using the most recent version of the Medical Dictionary for Regulatory Activities (MedDRA) coding dictionary

The analysis of AEs will be based on the concept of treatment emergent adverse events (TEAE). That means that all adverse events occurring 'on treatment' as outlined in [Section 6.7](#) will be considered as TEAE.

All AEs occurring before 'on treatment' will be assigned to 'screening' and all AEs occurring after 'on treatment' will be assigned to 'post-treatment'. In general, AEs attributed to 'Screening' or 'Post-treatment' will be listed only.

An overall summary of AEs will be presented.

Frequencies [N (%)] of patients with AEs will be summarised by treatment, primary system organ class and preferred term (using MedDRA). Separate tables will be provided for patients with serious adverse events.

The system organ classes will be sorted according to the standard sort order specified by European medicines agency (EMA), preferred terms will be sorted by frequency (within system organ class). The severity of AEs will be summarised by the maximum intensity of the events each patient had. This will show the number and percent of patients who had at most mild, moderate, severe, and life threatening events. Severe AEs is defined as an AE with mild, moderate, severe grade.

Additionally, the following analyses will be reported for disclosure on European Union Drug Regulating Authorities Clinical Trials Database (EudraCT) and clinicaltrials.gov:

- Frequency [N(%)] of patients with non-serious AEs occurring with incidence in preferred term greater than 5% by treatment,
- AEs per arm for disclosure on EudraCT by treatment
- Non-serious AEs for disclosure on EudraCT by treatment
- Serious AEs for disclosure on EudraCT by treatment

Adverse events of interest

All endpoints related to safety, outlined in [Section 5.2.2](#) and [Section 5.3](#), are clearly marked as such. In particular, endpoints related to MBE, Stroke, MI, PE and DVT. There is no further description below on how they should be analysed, however, they will be summarized with the safety data under the topic of 'AEs of special interest'.

There are two other AEs of special interest, which are not mentioned in Sections 5.2.2 and 5.3:

- Transient ischemic attack
- Systemic embolism

AEs recorded on the AE page of the CRF, indicated as such via the relevant tick box, will be grouped and summarized using frequency tables.

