The favorable results on the primary endpoint in the alteplase 0.6/0.04 mg/kg dosing group were supported by similar trends for other prespecified analyses, including sensitivity analyses of the primary endpoint, as well as secondary efficacy endpoints of lower all-cause mortality and lower all-cause mortality or mechanical ventilation up to Day 28 compared with the SOC group, greater improvement in median $\text{PaO}_2/\text{FiO}_2$ ratio from baseline to Day 6 and more ventilator-free days from the start of treatment to Day 28 than in the alteplase 0.3/0.02 mg/kg and SOC groups.

A Kaplan-Meier estimate of the unadjusted primary analysis showed a separation of the alteplase 0.6/0.04 mg/kg group compared with the other two treatment groups, beginning at approximately Day 11. The risk difference for the alteplase 0.6/0.04 mg/kg group compared with the SOC group at Day 28 was 19.1% in favour of alteplase (95% CI -10.6%, 48.8%).

[REDACTED]

Secondary and further endpoint results supported the clinical benefit of alteplase in addition to SOC, particularly for the alteplase 0.6/0.04 mg/kg group. Both alteplase groups had numerically fewer cases of all-cause mortality than in the SOC group at Day 28. All-cause mortality or mechanical ventilation at Day 28 was considered as treatment failure; both alteplase groups had fewer cases of all-cause mortality or mechanical ventilation at Day 28 than the SOC group. The alteplase 0.6/0.04 mg/kg group had more ventilator-free days from the start of treatment to Day 28 than the alteplase 0.3/0.02 mg/kg and SOC groups. In addition, the alteplase 0.6/0.04 mg/kg group had a greater improvement in median $\text{PaO}_2/\text{FiO}_2$ ratio from baseline to Day 6 compared with the alteplase 0.3/0.02 mg/kg or SOC group..

[REDACTED]

Safety

The overall safety results were generally comparable across the treatment groups. Patients treated with alteplase and those receiving only standard of care had similar frequencies of any adverse events (AEs), severe AEs, and serious AEs. The majority of reported AEs were of mild or moderate intensity. No new safety signals were identified.

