5.2.6.1.5 Intensity (severity) of Adverse events

The intensity (severity) of the AE should be judged based on the following:

Mild:	Awareness of sign(s) or symptom(s) that is/are easily tolerated.
Moderate:	Sufficient discomfort to cause interference with usual activity.
Severe:	Incapacitating or causing inability to work or to perform usual activities.

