7.2.5 Safety analyses

Adverse events will be coded using the Medical Dictionary for Drug Regulatory Activities (MedDRA). Standard BI summary tables and listings will be produced. All adverse events with an onset between start of treatment and end of the REP, as defined in [Section 1.2.](#), will be assigned to the on-treatment period for evaluation.

All treated patients will be included in the safety analysis. In general, safety analyses will be descriptive in nature and will be based on BI standards. No hypothesis testing is planned.

Statistical analysis and reporting of adverse events will concentrate on treatment-emergent adverse events, i.e. all adverse events occurring between start of treatment and end of the REP. Adverse events that start before first drug administration and deteriorate under treatment will also be considered as 'treatment-emergent'.

Frequency, severity, and causal relationship of adverse events will be tabulated by system organ class and preferred term after coding according to the current version of MedDRA at DBL.

Laboratory data will be analysed quantitatively and qualitatively. The latter will be done via comparison of laboratory data to their reference ranges. Values outside the reference range as well as values defined as clinically relevant will be summarised. Treatment arms will be compared descriptively with regard to distribution parameters as well as with regard to frequency and percentage of patients with abnormal values or clinically relevant abnormal values.

Vital signs, physical examinations, or other safety-relevant data observed at screening, baseline, during the course of the trial and at the end-of-trial evaluation will be assessed with regard to possible changes compared with findings before start of treatment.

Further details on the safety analysis will be specified in the TSAP.

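### The Part 1 SAP defines a severe adverse event so that mild and moderate events count as severe; the rule needs correcting, but nothing shows that it produced the Part 1 results

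*SAP*

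**What the plan says.** Protocol 5.2.6.1.5 grades AE intensity as mild, moderate or severe. *Severe* is a grade of its own: "Incapacitating or causing inability to work or to perform usual activities". Protocol 7.2.5 commits to showing intensity: "Frequency, severity, and causal relationship of adverse events will be tabulated by system organ class and preferred term".

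The Part 1 SAP, section 7.8.1, deals with intensity in three consecutive sentences:

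- the method: "The severity of AEs will be summarised by the maximum intensity of the events each patient had";
- the display: "This will show the number and percent of patients who had at most mild, moderate, severe, and life threatening events";
- the definition: "Severe AEs is defined as an AE with mild, moderate, severe grade".

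Its parent section, 7.8, adds: "The safety analysis will be performed as outlined in the CTP, according to BI standards and on the TS".

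Protocol 1.1, summarising Part 1 safety, says that alteplase and standard-of-care patients "had similar frequencies of any adverse events (AEs), severe AEs, and serious AEs". The next sentence reads: "The majority of reported AEs were of mild or moderate intensity".

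Section 7.8.1 of the Part 2 SAP has no intensity table and no definition of a severe AE. Its section 4, which lists changes to the planned analysis, does not mention the omission.

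**The concern.** A definition of a severe AE has to separate severe events from the rest. This one lists every grade that the protocol has, so it does not depend on intensity. A severe-AE row built on it could not show an excess of severe events in either arm beyond what the any-AE row already shows.

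The term is also used. Protocol 1.1 cites similar frequencies of severe AEs in a summary that ends by supporting continuation into Part 2. That summary gives counts by arm for the commonest organ classes, for the more frequent serious AEs and for bleeding, but none for severe AEs. A reader who wants to know what was counted finds only one written definition of a severe AE in the two SAPs, and it is the faulty one. The Part 1 SAP history table shows that section 7.8.1 was edited for version 2.0 and the sentence stayed in.

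**Working it through.** The plan gives no figure to reproduce, and the documents give no severe-AE or any-AE count by arm. The check is a comparison of definitions.

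**Step 1. Set the scales and the rule side by side.**

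| Grade | On the protocol scale (5.2.6.1.5)? | In the Part 1 SAP display (7.8.1)? | Counted as severe by the SAP rule? | Severe by the protocol? |
|---|---|---|---|---|
| Mild | yes | yes | yes | no |
| Moderate | yes | yes | yes | no |
| Severe | yes | yes | yes | yes |
| Life threatening | no | yes | no | no such grade |

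**Step 2. Apply the rule on the protocol scale.** The rule's set is {mild, moderate, severe} and the protocol's set of grades is {mild, moderate, severe}. The two sets are equal. Each patient with at least one graded AE therefore has at least one severe AE under the rule, so P(severe AE | any graded AE) = 1 in every arm, whatever the treatment does. The difference between arms in severe AEs equals the difference in any graded AE.

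**Step 3. Apply it on the SAP's own four levels.** The grades left out are {mild, moderate, severe, life threatening} minus {mild, moderate, severe} = {life threatening}. A patient with one mild event counts as having a severe AE. A patient whose only event is life threatening does not. The rule no longer captures every graded event here, but it is still wrong, and at both ends of the scale.

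**Step 4. See what the rest of the paragraph provides.** The maximum-intensity summary places each patient at the highest grade reached. It keeps mild, moderate and severe apart however the definition sentence is read, so an excess of severe events in one arm would be visible there. The defect is confined to a separate severe-AE row.

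**Step 5. Ask whether the literal rule was used.** Protocol 1.1 names any, severe and serious AEs as three separate categories and says that mild or moderate events were the majority. Under the literal rule the first two categories would be identical on the protocol scale. The wording therefore points to grades that were kept apart. It is not proof, because no counts are shown.

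**Step 6. Check Part 2.** Protocol 7.2.5 requires severity to be tabulated. Part 2 SAP 7.8 says that the safety analysis follows the protocol and sponsor standards, so the obligation is carried by reference. Section 7.8.1, where the displays are listed, does not name the table or define the term.

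**The case against.** The strongest reply is that this is one garbled sentence with no demonstrated effect. The SAP defers to the protocol for the safety analysis, and the protocol defines *severe* properly. The sentence may be a slip in which *Severity* was meant, so that it merely lists grades. The maximum-intensity table in the same paragraph does the discriminating work. The results text treats severe AEs as a category of their own. Part 1 was exploratory, with about 60 patients, and an independent data monitoring committee reviewed the unblinded safety data before recommending continuation. The Part 2 SAP has already lost the sentence.

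Most of this stands, and it limits the consequence. It does not remove the error. The slip reading is an inference, the deferral to the protocol leaves two conflicting definitions in force, and the absence of counts means that a reader cannot settle which one was used. On Part 2, it is fair that leaving the table out of 7.8.1 does not by itself contradict the protocol. It is still a gap in a section meant to say what will be produced.

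A reader might infer that the comparison cited in protocol 1.1 cannot discriminate between arms, and so should be withdrawn. The documents do not support that: nothing shows that the literal rule generated the Part 1 tables, and the evidence in step 5 leans the other way.

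**Conclusion.** The definition is wrong as written, on the protocol's three grades and on the SAP's four-level display, and the life-threatening level has no counterpart in the protocol scale. If the rule was followed literally with the protocol's grades, a severe-AE row would add nothing to the any-AE row. That condition is not shown to hold, and the planned maximum-intensity table separates the grades either way.

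The size of any effect on reported Part 1 results cannot be stated, because the counts are absent. Any pair of true severe-AE rates put forward to illustrate the loss would be an assumption.

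A reader might also infer that the faulty rule will contaminate the pooled Part 1 and Part 2 output. Protocol 7.2.1 plans descriptive pooling of most endpoints, and the Part 2 SAP assigns the pooled analyses to a separate abbreviated plan that is not among the documents. Nothing shows that the sentence carries over.

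The scope is descriptive safety output. No confirmatory test, error rate or sample size is affected. The point is small, but it concerns an analysis rule and is worth correcting.

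**What to change.** 1. Define a severe AE as an AE whose intensity is *severe* on the protocol 5.2.6.1.5 scale. Part 1 has already been analysed, so record this as a documented correction to Part 1 SAP 7.8.1 and put the same definition in Part 2 SAP 7.8.1.
2. Reconcile the life-threatening level with the protocol scale, or remove it from the display.
3. Name the maximum-intensity table by arm in Part 2 SAP 7.8.1, so that the severity tabulation required by protocol 7.2.5 is listed where the displays are specified.
4. Confirm which definition lies behind the statement on severe AEs in protocol 1.1, and give the counts by arm there. Re-derive them only if the literal rule was applied.

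The cost is a few lines of SAP text, one named table and one sentence with counts in the protocol summary. The intensity grades have already been reported on for Part 1, so no new data are needed. If a re-derivation proves necessary, it is one table.
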